5.4 Blinding and procedures for unblinding the study (Not applicable)

5.5 Treatments

5.5.1 Identity of investigational product

Table 4 Formulation of Investigational Product

Investigational product	Dosage form and strength	Manufacturer
AZD9291	20 mg Solution formulation containing a nominal 1 μ Ci activity ^{a,b} (¹⁴ C]-labelled and unlabelled should add up to this quantity based on desired activity)	AstraZeneca
Solution buffer	0.01M citrate buffer pH 3.5	

^a The container must be kept for quantification of residual radioactivity.

^b Once the volunteer has consumed the initial preparation of 100 mL, a further 100 mL of purified water must be used to rinse the container twice (2x50 mL) and administered to the volunteer. The total fluid volume administered will be 240 mL of fluids (buffer and water) inclusive of the volume of solution administered and any rinses.

5.5.2 Doses and treatment regimens

Each volunteer will receive a single dose of 20 mg [¹⁴C]-AZD9291 oral solution (free base equivalent) containing a nominal dose 1 μ Ci (0.037 MBq) activity as a single administration on Day 1. [¹⁴C]-AZD9291 will be administered with 240 mL of fluids (buffer and water) inclusive of the volume of solution administered and any rinses.

Volunteers should be fasted overnight for 10 hours prior to investigational product administration (water is allowed up to 1 hour prior to investigational product administration). Volunteers must remain fasted for 4 hours after investigational product administration. Water is allowed 1 hour after investigational product administration.

5.5.3 Labelling

Labels will be prepared in accordance with Good Manufacturing Practice (GMP) and local regulatory guidelines. The labels will fulfil GMP Annex 13 requirements for labelling.

5.5.4 Storage

All investigational products should be kept in a secure place under appropriate storage conditions. The investigational product label specifies the appropriate storage.

5.6 Concomitant and poststudy treatment(s)

Volunteers should abstain from taking any prescribed medication, over-the-counter remedies, herbal medications, high-dose or 'mega' vitamins, mineral supplements, or medicines purchased via the Internet beginning 4 weeks (or longer depending on the medication's

half-life) before investigational product administration and continuing until 3 months after investigational product administration. Paracetamol 1 g, every 6 hours, to a maximum daily dose of 4 g is permitted; however, the Principal Investigator should be informed so this can be recorded in the volunteer's paper Case Report Form (pCRF).

Other medication, which is considered necessary for the volunteer's safety and well being, may be administered at the discretion of the Principal Investigator and recorded in the appropriate sections of the pCRF.

5.7 Treatment compliance

The date and time of administration of the investigational product should be recorded in the appropriate sections of the pCRF. In order to ensure treatment compliance, the administration of the investigational product will be performed under the supervision of the study personnel.

5.7.1 Accountability

The investigational product provided for this study will be used only as directed in this CSP. The investigational product will be administered under supervision.

Study centre personnel will account for all investigational product received, all unused investigational product, and for appropriate destruction of unused investigational product. Destruction must not take place unless the responsible person at AstraZeneca has approved it. Certificates of delivery, destruction, and return should be signed.

5.8 Discontinuation of investigational product (Not applicable)

5.9 Withdrawal from study

Volunteers are at any time free to withdraw from the study (investigational product and assessments), without prejudice to further treatment (withdrawal of consent). These volunteers will always be asked about the reason(s) and the presence of any AEs. If possible, they will be seen and assessed by the Principal Investigator. Adverse events will be followed up (Sections [6.3.3](#) and [6.3.4](#)).

Withdrawn volunteers will not be replaced.

6. COLLECTION OF STUDY VARIABLES

The study assessments are described in the sections below. The study plan and timing of these assessments are detailed in [Table 2](#) and [Table 3](#). Additional assessments may be performed if the Principal Investigator considers them necessary for volunteer safety.

It is important that PK sampling occurs as close as possible to the scheduled time. In order to achieve this, other assessments scheduled at the same time may be initiated prior to the time point. The sequence at a particular time point is:

1. 12-lead ECG.
2. Vital signs (blood pressure and pulse rate).
3. PK blood sample.
4. Safety laboratory assessment blood sample.
5. PK urine sample.

Apart from the predose PK blood sampling, which should occur within 30 minutes prior to investigational product administration, other predose assessments may be performed up to 60 minutes prior to administration of the investigational product.

For occasions when more than one assessment is required at a particular time point, PK blood samples should be prioritised. Additional assessments may be performed if the Principal Investigator considers them necessary for volunteer safety.

6.1 Recording of data

The Principal Investigator will ensure that data are recorded on the pCRF as specified in the study protocol and in accordance with the instructions provided.

The Principal Investigator ensures the accuracy, completeness, legibility, and timeliness of the data recorded and of the provision of answers to data queries according to the Clinical Study Agreement (CSA). The Principal Investigator will sign the completed pCRF. A copy of the completed pCRF will be archived at the study centre.

6.2 Data collection at enrolment and follow-up

Following a signed informed consent, volunteers will be screened for eligibility to be enrolled in the study.

6.2.1 Enrolment procedures

At enrolment each potential volunteer will provide written informed consent prior to starting any study-specific procedures.

Demographic data and other characteristics will be recorded and will include date of birth, gender, race, ethnicity, and alcohol consumption.

Each volunteer will undergo screening in the 28 days prior to investigational product administration. This will consist of:

- Obtaining written informed consent prior to starting any study-specific procedures
- Recording demographic data – date of birth, gender, race, and ethnicity
- Height, weight, and calculation of BMI
- A standard medical, medication, and surgical history with review of the inclusion and exclusion criteria with the volunteer
- A complete physical examination
- Habits of nicotine and alcohol use
- Vital signs measurements (supine pulse rate and blood pressure)
- Recording of 12-lead paper ECG
- A blood sample for routine clinical chemistry and haematology as well as a screen for hepatitis B surface antigen, antibodies to hepatitis C virus, and antibodies to HIV
- A urine sample for routine urinalysis and drugs of abuse screen (including carbon monoxide and alcohol)
- Assessment of any SAEs
- Assessment of any prior and/or concomitant medication use
- Ophthalmic examination

6.2.2 Follow-up procedures

The final medical assessment on Day 84 or on the last day of urine/faecal collection (whichever is later) will include the assessment of concomitant medication, complete physical examination, clinical chemistry, haematology, PK blood collection, urinalysis, urine and faeces collection, supine blood pressure and pulse rate, weight, 12-lead ECG, and recording of AEs/SAEs.

6.3 Safety

The Principal Investigator is responsible for ensuring that all staff involved in the study is familiar with the content of this section.

6.3.1 Definition of adverse events

An AE is the development of an undesirable medical condition or the deterioration of a pre-existing medical condition following or during exposure to a pharmaceutical product, whether or not considered causally related to the product. An undesirable medical condition can be symptoms (eg, nausea, chest pain), signs (eg, tachycardia, enlarged liver), or the abnormal results of an investigation (eg, laboratory findings, ECG). In clinical studies, an AE can include an undesirable medical condition occurring at any time, including run-in or washout periods, even if no study treatment has been administered.

6.3.2 Definitions of serious adverse event

An SAE is an AE occurring during any study phase (ie, run-in, treatment, washout, follow-up), that fulfils one or more of the following criteria:

- Results in death
- Is immediately life-threatening
- Requires inpatient hospitalisation or prolongation of existing hospitalisation
- Results in persistent or significant disability/incapacity or substantial disruption of the ability to conduct normal life functions
- Is a congenital abnormality or birth defect
- Is an important medical event that may jeopardise the volunteer or may require medical intervention to prevent one of the outcomes listed above

For further guidance on the definition of an SAE, see [Appendix B](#) to this CSP.

6.3.3 Recording of adverse events

Time period for collection of adverse events

Only SAEs will be collected from screening until the End of Study visit (Day 85) whereas AEs will be collected from Day -1 through to the End of Study visit (Day 85).

Follow-up of unresolved adverse events

Any AEs that are unresolved at the volunteer's End of Study visit, should be followed up by the Principal Investigator for as long as medically indicated, but without further recording in the pCRF. AstraZeneca retains the right to request additional information for any volunteer with ongoing AE(s)/SAE(s) at the end of the study, if judged necessary.

Variables

The following variables will be collect for each AE:

- AE (verbatim)

- The date and time when the AE started and stopped
- Maximum intensity, rated according to the following scale:
 - Mild (awareness of sign or symptom, but easily tolerated)
 - Moderate (discomfort sufficient to cause interference with normal activities)
 - Severe (incapacitating, with inability to perform normal activities)
- Whether the AE is serious or not
- Principal Investigator causality rating against the investigational product (yes or no)
- Action taken with regard to investigational product
- Whether AE caused volunteer's withdrawal from study (yes or no)
- Outcome

In addition, the following variables will be collected for SAEs:

- Date AE met criteria for SAE
- Date Principal Investigator became aware of SAE
- AE is serious due to
- Date of hospitalisation
- Date of discharge
- Probable cause of death
- Date of death
- Autopsy performed
- Causality assessment in relation to study procedure(s)
- Causality assessment in relation to other medication
- Description of AE

It is important to distinguish between serious and severe AEs. Severity is a measure of intensity whereas seriousness is defined by the criteria in Section 6.3.2. An AE of severe intensity need not necessarily be considered serious. For example, nausea that persists for

several hours may be considered severe nausea, but not an SAE. On the other hand, a stroke that results in only a limited degree of disability may be considered a mild stroke but would be an SAE.

Causality collection

The Principal Investigator will assess causal relationship between investigational product and each AE, and answer 'yes' or 'no' to the question 'Do you consider that there is a reasonable possibility that the event may have been caused by the investigational product?'

For SAEs, causal relationship will also be assessed for other medication and study procedures. Note that for SAEs that could be associated with any study procedure, the causal relationship is implied as 'yes'.

A guide to the interpretation of the causality question is found in [Appendix B](#) to this CSP.

Adverse Events based on signs and symptoms

All AEs spontaneously reported by the volunteer or reported in response to the open question from the study personnel: 'Have you had any health problems since the previous visit/you were last asked?', or revealed by observation will be collected and recorded in the pCRF. When collecting AEs, the recording of diagnoses is preferred (when possible) to recording a list of signs and symptoms. However, if a diagnosis is known and there are other signs or symptoms that are not generally part of the diagnosis, the diagnosis and each sign or symptom will be recorded separately.

Adverse Events based on examinations and tests

The results from protocol-mandated laboratory tests and vital signs will be summarised in the CSR. Deterioration as compared to baseline in protocol-mandated laboratory values, vital signs, or other safety variables should therefore only be reported as AEs if they fulfil any of the SAE criteria or are the reason for discontinuation of treatment with the investigational product.

If deterioration in a laboratory value/vital sign is associated with clinical signs and symptoms, the sign or symptom will be reported as an AE and the associated laboratory result/vital sign will be considered as additional information. Wherever possible the reporting Principal Investigator uses the clinical, rather than the laboratory term (eg, anaemia versus low haemoglobin value). In the absence of clinical signs or symptoms, clinically relevant deteriorations in nonmandated parameters should be reported as AE(s).

Any new or aggravated clinically relevant abnormal medical finding at a physical examination as compared with the baseline assessment will be reported as an AE.

NB. Cases where a volunteer shows an aspartate aminotransferase (AST) **or** alanine aminotransferase (ALT) ≥ 3 times the upper limit of normal (ULN) **or** total bilirubin ≥ 2 times the ULN may need to be reported as SAEs, please refer to [Appendix D](#) 'Actions required in

cases of combined increase of aminotransferase and total bilirubin – Hy’s Law’, for further instructions.

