c Blood sampling for genotyping is optional and will be collected if the volunteer provides additional informed consent on Day -1.

d Height/weight will be evaluated at the screening visit. Only weight will be evaluated on Day-1 and Day 84 (End of Study visit).

e A brief physical examination (including general appearance, skin, abdomen, cardiovascular system, and lungs) performed at admission or predose.

- f The volunteers will fast from overnight prior to clinical laboratory evaluations at screening. Postdose time points will be Days 7, 14, 28 and End of Study visit (not fasted).
- g Creatinine clearance will be estimated using the Cockcroft-Gault formula at screening.
- h Ophthalmic examination (best corrected visual acuity and slit-lamp fundoscopy and intraocular pressure measurement) will be conducted at screening (will be considered the baseline value; no need to repeat) and for cause (on occurrence of AE only).
- i A sample for urinalysis to be collected together with the other clinical laboratory evaluations. Microscopy will only be performed if abnormal urinalysis results are observed.
- j Alcohol will be assessed by an alcohol breath test. Smoking will be assessed by performing a breath carbon monoxide test. A positive test will constitute a value of greater than 10 ppm.
- k Supine blood pressure and pulse rate will be evaluated after the volunteer has rested in a supine position for at least 10 minutes. If possible, the same arm and equipment should be used for each evaluation (refer to [Table 3](#) for time points).
- l Refer to [Table 3](#) for ECG time points.
- m Volunteers will receive a single administration of the investigational product on Day 1.
- n Blood, plasma, urine and faeces samples will be collected (refer to [Table 3](#) for time points).
- o Discharge on Day 85.
- p Only SAEs will be collected from screening until the End of Study visit whereas AEs will be collected from Day -1 through to the End of Study Visit.

Table 3 **Schedule of assessments**

Time (Day/hours)	12-lead ECG	P & BP^a	Safety blood & urine^c	24-hour urine collection^b	Faecal collection^b	PK and Met-ID Blood/plasma	Food and Fluid Restrictions^c	Physical examination	Residency
Screening ^d	X	X	X					X	
Day -1 ^{d,e}							F ^f	X ⁱ	T
Predose	X ^g	X	X	T	T	X	D ^h	X ^j	
Dose (Day 1)							D		
0.5						X			
1	X	X				X	D ^h		
1.5						X			
2	X	X				X			
3						X			
4	X	X				X	F ^f , M		
6						X	F		
8	X	X				X			
10						X			
12	X	X				X			
18						X			

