6.3.7 Resting 12-lead electrocardiogram

Twelve-lead ECGs will be recorded at the time points indicated in the study plan ([Table 2](#) and [Table 3](#)).

Electrocardiograms will be recorded in the supine position after the volunteer has rested in this position for at least 10 minutes. A total of 3 12-lead ECG will be recorded at 10 minute intervals at predose and 24-hours postdose.

Only the overall evaluation (normal/abnormal) will be captured in the pCRF. Any abnormalities (including corrected QT interval [QTc] values) should be reviewed by an appropriately qualified person.

The original ECG printouts with variables must be signed and dated and stored in the volunteer’s source workbook as source data.

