12.2.3 Safety and tolerability measurements

All safety data (scheduled and unscheduled) will be presented in the data listings.

Safety variables (eg, clinical laboratory values and vital signs) will be reported to the same precision as the source data. Derived variables will be reported using similar precision to those from which they were derived (eg, QTcF derived from QT interval).

All AEs and clinical laboratory outliers that occur following the first dose of study medication will be included in the tabulations of AEs and outlier events, including episodes that occur at unscheduled evaluations.

All available data from volunteers in the safety analysis set will be included in the safety analyses. No adjustment or imputation will be utilised for missing values or for volunteers who withdraw prior to completing the study, neither will analyses be restricted to volunteers with complete data.

Adverse events beginning at or after the first dose of investigational product will be summarised by Preferred Term and System Organ Class using the Medical Dictionary for Regulatory Activities (MedDRA) vocabulary by treatment and across all treatments. Adverse events that begin during the washout periods will be assigned to the last treatment received prior to the onset of the AE. Furthermore, listings of SAEs and AEs that lead to withdrawal will be made and the number of volunteers who have any AEs, SAEs, AEs that lead to withdrawal, and AEs with severe intensity will be summarised.

Tabulations and listings of data for vital signs and clinical laboratory tests will be presented, as appropriate. All continuous safety data will be summarised by treatment and/or across all treatments, as appropriate, for the observed value at each scheduled assessment and for the corresponding change from baseline. For clinical laboratory tests, listings of values for each volunteer will be presented with abnormal or out-of-range values flagged. Clinical laboratory data will be reported in Système International units in the CSR.

Results from the physical examinations, ECGs, and ophthalmologic examinations will be presented in listings only.

Extra measurements (such as unscheduled or repeat assessments) will not be included in the descriptive statistics, but will be included in subject listings.

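### One of the two AE triggers for mandated safety tests cannot operate in this single-dose study, and the reason given for the restriction does not cover ECGs

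*Protocol*

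**What the plan says.** Section 6.3.3 of the protocol first states that mandated laboratory and vital-sign results will be summarised in the clinical study report. It concludes that deterioration from baseline in these, or in other safety variables, should "only be reported as AEs if they fulfil any of the SAE criteria or are the reason for discontinuation of treatment with the investigational product".

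The same section adds two further rules. Where a laboratory or vital-sign change comes with clinical signs or symptoms, "the sign or symptom will be reported as an AE and the associated laboratory result/vital sign will be considered as additional information". Where there are no signs or symptoms, "clinically relevant deteriorations in nonmandated parameters should be reported as AE(s").

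The general definition in Section 6.3.1 counts "abnormal results of an investigation (eg, laboratory findings, ECG") among the conditions that can be an AE.

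On dosing, a footnote to Table 2 (Section 3.1) says "Volunteers will receive a single administration of the investigational product on Day 1". The heading of Section 5.8 is all that the protocol says about stopping the product: "5.8 Discontinuation of investigational product (Not applicable").

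On ECGs, Section 6.3.7 says "Only the overall evaluation (normal/abnormal) will be captured in the pCRF", and Section 12.2.3 says "Results from the physical examinations, ECGs, and ophthalmologic examinations will be presented in listings only".

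**The concern.** A rule with two triggers, one of which depends on stopping a product that is taken once, has in effect one trigger. It reads like wording carried over from a multiple-dose study. What remains is that an isolated change in a mandated test is an AE only if it is serious.

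Safety and tolerability is a secondary objective (Section 2.2), and AEs are one of its listed endpoints. An AE record carries items that no table or listing of test values supplies: the investigator's causality judgement, maximum intensity, outcome, and whether the event caused withdrawal. Section 1.4.2 reports some evidence of QT prolongation and slower heart rate in guinea pigs and dogs (marginal, transient and not dose-related in dog telemetry), and higher blood pressure in rat and guinea pig. Changes of that kind can occur without symptoms, in variables to which the restriction applies.

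**Working it through.** The protocol gives no figure to reproduce. The check is a reading of the provisions against each other.

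1. **The rule.** Under Section 6.3.3, a deterioration in a mandated variable is an AE if it is (a) serious or (b) the reason for discontinuing the product.

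2. **Can (b) occur?** There is one administration, on Day 1 (Table 2 footnote; Section 5.5.2). Every post-baseline value comes after it, and Section 5.8 declares discontinuation not applicable. So (b) is empty and the rule reduces to (a).

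3. **Does withdrawal from the study fill the gap?** No. Section 5.9 treats withdrawal separately, and 6.3.3 collects whether an AE caused it, but the restricting sentence names discontinuation of the product. A non-serious, asymptomatic laboratory change that led to withdrawal would not be an AE under that sentence. It would then also be absent from the listing in Section 12.2.3 of AEs leading to withdrawal.

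4. **Against the definition.** Section 6.3.1 includes abnormal laboratory and ECG results in the definition of an AE. Section 6.3.3 excludes the non-serious, asymptomatic ones when the test is mandated, but includes clinically relevant ones when it is not. A variable that the protocol chose to monitor has the narrower rule.

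5. **Does the stated reason cover each variable?**
   - Laboratory values: yes. Section 12.2.3 summarises observed values and change from baseline, tabulates outliers and flags out-of-range values in listings.
   - Vital signs: yes for scheduled values. Unscheduled and repeat measurements are listed but left out of the descriptive statistics.
   - ECG: no. The case report form holds only normal or abnormal (6.3.7) and the results are listed, not summarised (12.2.3). Section 11.1.1 does name a baseline for ECG change, but with no interval value captured in the form, and with reporting by listing only, that does not produce a summary.

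6. **AE routes that remain open.** Accompanying signs or symptoms (6.3.3), clinically relevant new or aggravated physical-examination findings (6.3.3), ophthalmological abnormalities (6.3.9), and anything meeting a seriousness criterion, including the important-medical-event criterion (6.3.2). Liver changes have their own pathway in Appendix D.

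7. **How much data the ECG gap touches.** Table 3 schedules post-dose ECGs at 1, 2, 4, 8, 12 and 24 hours, on Days 7, 14 and 21, and at discharge on Day 85, which is 10 times. With 8 volunteers that is 8 × 10 = 80 scheduled assessments. This counts the assessments subject to the restriction. It does not estimate AEs lost, because the protocol gives no rate of asymptomatic ECG change.

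**The case against.** The strongest reply is that for laboratory values and vital signs the restriction is a deliberate convention with a stated reason: the results are reported elsewhere, so making each change an AE would count it twice. In a multiple-dose study, a non-serious, asymptomatic change that did not stop treatment would not be an AE either, so the void trigger alters little. This stands. It is why the broader remedy, making every clinically relevant laboratory or vital-sign change an AE, would reverse a choice rather than repair a fault.

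The second reply is that the information is kept. Suspected clinically significant laboratory values are repeated and, if confirmed in an enrolled volunteer, followed (6.3.5). Laboratory, vital-sign and ECG data are reviewed by a sponsor expert for other significant AEs (11.1.2). ECG abnormalities are reviewed by a qualified person (6.3.7). With 8 volunteers, a full listing shows every recorded result. This also largely stands. However, the review under 11.1.2 rests on the sponsor's judgement and does not supply the investigator's causality, intensity and outcome. The listed ECG result is only normal or abnormal.

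A third reply is that the intensity scale in 6.3.3 is worded around awareness and interference with activities, so it suits asymptomatic changes poorly. That is fair for intensity. It does not apply to causality, outcome or the withdrawal field.

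A reader might infer that non-serious deterioration in mandated safety variables is never recorded at all, or that the tolerability profile is materially biased. The protocol supports neither. The open routes in step 6 and the summaries in step 5 contradict the first. For the second, nothing in the protocol makes AE counts the main safety summary, since the synopsis lists AEs beside vital signs, examinations, ECGs and laboratory assessments.

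**Conclusion.** The point holds in a narrow form and is minor. The discontinuation trigger in 6.3.3 is void, so an isolated, asymptomatic, non-serious deterioration in a mandated laboratory value, vital sign or ECG cannot be reported as an AE, even when it leads to withdrawal. That contradicts 6.3.1, and for ECGs the stated justification fails. The loss is mainly from the AE tables and not from the study data. Its direction is known, since AE counts can only be lower. Its size is not, because the protocol gives no expected frequency of such changes. It may be zero among 8 volunteers.

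The conclusion rests on two readings: that ECGs fall under the other safety variables named in 6.3.3, and that discontinuation of treatment there means stopping the product, as the sentence says, and not leaving the study. If the second was meant loosely as withdrawal, the withdrawal part of the point falls away once the wording says so. The ECG part remains.

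**What to change.** Reconcile Sections 5.8, 6.3.1 and 6.3.3 with two changes to one sentence of 6.3.3, and a cross-reference:

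- Replace the discontinuation trigger with the deterioration being the reason for withdrawal from the study. This matches a field already collected for each AE in 6.3.3 and a listing already planned in 12.2.3.
- Confine the restriction to laboratory values and vital signs, the variables that are in fact summarised. Clinically relevant ECG deterioration then becomes reportable as an AE, on the standard 6.3.3 already uses for non-mandated parameters.
- In 6.3.1, point to 6.3.3 so that the general definition and the narrower rule for laboratory values and vital signs no longer conflict.

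The cost is a few extra AE records, some perhaps incidental. Dosing, visits, assessments and the planned summaries do not change. Extending the clinically relevant standard to laboratory values and vital signs as well is an option, but a trade-off against the double reporting that the present convention avoids, and this point does not require it.
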